5.10.4. POST-PROCEDURE VISIT

The Post-Procedure visit is applicable for attempt subjects and procedure subjects.

The post-procedure visit will occur per standard of care but not to exceed 2 days from the end of the study procedure. The data collection requirements of the post procedure visit are outlined below:

- Date of visit
- Physical assessment (incl. vital signs and 12-lead ECG)
- Changes in Medications Regimen

**LUMINIZE_CLINICAL PROTOCOL**Document ID: VER-DOC-527
Controlled Document: VER-SIGN-3084TEMPLATE:
ONEPROJECTS/SIGN-267

Version: 4.0

Project: VERAFYE (VER)
Date: 22-Nov-2024 14:16:10
Page: 28 / 51

- Adverse Events, if applicable
- Protocol Deviations, if applicable

5.10.5. 7-DAY FOLLOW-UP

The 7-day follow-up is applicable for attempt subjects and procedure subjects.

If the patient was discharged prior to the day 7 follow-up, a telephone contact will occur. If the patient is still hospitalized at the time of the day 7 follow-up, the 7 days follow-up will be performed as an in-hospital visit. The data collection at the day 7 follow-up includes:

- Date of contact (visit/telephone call)
- Changes in Medication Regimen
- Adverse Events, if applicable
- Protocol Deviations, if applicable

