5.11.3. POTENTIAL ADVERSE EVENTS

Subjects participating in this study are subject to the same risks shared by all patients undergoing an ablation procedure for treatment of AFL or AF; or an LAA/ASD closure procedure.

Based upon the current literature, the tables below includes an alphabetical list of the possible anticipated adverse events and possible adverse device effects associated with ablation catheters and closure devices. Occurrence of any of the listed events could lead to prolonged hospitalization for the subject.

Table 4: Potential adverse events during catheter ablation procedures

Access site complications	Headache
Allergic reaction	Heart failure
Anemia	Hematoma
Arrhythmias	Hemothorax
Bleeding/Hemorrhage	Hemodynamic instability
Blurred vision	Hypertension/Hypotension
Cardiac perforation	Inadvertent injury to adjacent structures
Cardiac/pulmonary arrest	Infection
Catheter entrapment	Myocardial infarction
Cerebrovascular accident (CVA)	Nerve weakness/palsy/injury (i.e. phrenic/ vagus)
Chest discomfort/pain or pressure	Pericarditis
Complete heart block (transient/permanent)	Pneumothorax

**LUMINIZE_CLINICAL PROTOCOL**Document ID: VER-DOC-527
Controlled Document: VER-SIGN-3084TEMPLATE:
ONEPROJECTS/SIGN-267

Version: 4.0

Project: VERAFYE (VER)
Date: 22-Nov-2024 14:16:10
Page: 31 / 51

Complications of sedative agents/anesthesia/medications	Pseudoaneurysm
Coronary artery spasm	Pulmonary complications (i.e. edema, pulmonary hypertension, pleuritis, pneumonia)
Cough	Pulmonary vein stenosis
Death	Radiation injury/exposure
Diaphragmatic paralysis	Renal insufficiency/failure
Dizziness or lightheadedness	Respiratory Depression
Edema	Residual atrial septal defect (ASD)
Pericardial effusion/pleural effusion	Skin burns (i.e. radiation/defibrillator/ cardioverter)
Elevated cardiac enzymes	ST segment Elevation
Embolism (venous/arterial) (i.e. air, gas, thrombo, pulmonary)	Sore Throat
Endocarditis	Tamponade
Esophageal injury	Thrombus/thrombosis
Fever	Transient ischemic attack (TIA)
Exacerbation of existing conditions	Valvular damage
Fatigue	Vasospasm
Fistula (arterial-venous, atrial-esophageal)	Visual disturbances
Gastroparesis	Vasovagal reactions

Table 5: Potential adverse events during catheter closure procedures

Air embolism	Hemoptysis
--------------	------------

**LUMINIZE_CLINICAL_PROTOCOL**Document ID: VER-DOC-527
Controlled Document: VER-SIGN-3084TEMPLATE:
ONEPROJECTS/SIGN-267

Version: 4.0

Project: VERAFYE (VER)
Date: 22-Nov-2024 14:16:10

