	Provide all relevant source documentation (de-identified/pseudonymized) for reported event.	
When documentation is availableAt sponsor request.
Device Deficiencies (including but not limited to failures, malfunctions, and product nonconformities)	Complete Device Deficiencies CRF with all available new and updated information.	
Within 3 calendar days of first becoming aware of the event.Reporting required through the end of the study
	Provide all relevant source documentation (de-identified/pseudonymized) for reported event.	
Upon request of sponsor
Adverse Event including Adverse Device Effects	Complete AE CRF page, which contains such information as date of AE, treatment of AE resolution, assessment of seriousness and relationship to the device.	
In a timely manner after becoming aware of the informationReporting required through end of study
	Provide all relevant source documentation (de-	
Upon sponsor request

**LUMINIZE_CLINICAL PROTOCOL**Document ID: VER-DOC-527
Controlled Document: VER-SIGN-3084TEMPLATE:
ONEPROJECTS/SIGN-267

Version: 4.0

Project: VERAFYE (VER)
Date: 22-Nov-2024 14:16:10
Page: 39 / 51

Event Classification	Communication Method	Communication Timeline pre-market studies
	identified/pseudonymized) for reported event, as requested by sponsor.	

All events will be assessed by the investigator for relationship to study device and the study procedure.

Table 8: Relationship Events to Procedure/Device

Classification	Description

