Not Related	
Relationship to the device, comparator or procedures can be excluded when:
 
 - the event has no temporal relationship with the use of the investigational device or the procedures related to the use of the investigational device; - the serious event does not follow a known response pattern to the medical device (if the response pattern is previously known) and is biologically implausible; - the discontinuation of medical device application or the reduction of the level of activation/exposure - when clinically feasible – and reintroduction of its use (or increase of the level of activation/exposure), do not impact on the serious event; - the event involves a body-site or an organ that cannot be affected by the device or procedure; - the serious event can be attributed to another cause (e.g. an underlying or concurrent illness/ clinical condition, an effect of another device, drug, treatment or other risk factors); - the event does not depend on a false result given by the investigational device used for diagnosis, when applicable;

**LUMINIZE_CLINICAL PROTOCOL**Document ID: VER-DOC-527
Controlled Document: VER-SIGN-3084TEMPLATE:
ONEPROJECTS/SIGN-267

Version: 4.0

Project: VERAFYE (VER)
Date: 22-Nov-2024 14:16:10
Page: 40 / 51

Classification	Description
	In order to establish the non-relatedness, not all the criteria listed above might be met at the same time, depending on the type of device/procedures and the serious event.
Possibly Related	The relationship with the use of the investigational device or comparator, or the relationship with procedures is weak but cannot be ruled out completely. Alternative causes are also possible (e.g. an underlying or concurrent illness/ clinical condition or/and an effect of another device, drug or treatment). Cases where relatedness cannot be assessed or no information has been obtained should also be classified as possible.
Probably Related	The relationship with the use of the investigational device or comparator, or the relationship with procedures seems relevant and/or the event cannot be reasonably explained by another cause.

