5.13.2.0.2. Sponsor Reporting Requirements

The sponsor is responsible for reporting adverse event information to all participating Principal Investigators, ECs and regulatory authorities, as applicable. All events will be assessed by the Sponsor for relationship to study device and study procedure.

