5.14.6. STUDY INSURANCE

The Sponsor shall maintain clinical study insurance to provide coverage for the reasonable and necessary costs associated with the diagnosis and treatment of a research injury, defined as: "an illness or injury directly caused by the study product (drug/device) or study procedures required by the study protocol and would not have been expected from the standard treatment for a condition."

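### Causality is rated against an undefined, undivided 'study procedure', so within that rating harm from VERAFEYE-specific steps cannot be told from harm of the background ablation or closure

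*Combined protocol and SAP*

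**What the plan says.** Section 5.13.2.0.1 sets two causality ratings for the investigator: "All events will be assessed by the investigator for relationship to study device and the study procedure". Section 5.13.2.0.2 repeats them for the sponsor: "All events will be assessed by the Sponsor for relationship to study device and study procedure". Neither section, nor the definitions in Table 6, says what the study procedure is.

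Table 8 gives the criteria. Its 'Not Related' row opens without restriction: "Relationship to the device, comparator or procedures can be excluded when". The first criterion beneath is narrower: "the event has no temporal relationship with the use of the investigational device or the procedures related to the use of the investigational device". A later criterion in that row accepts as an alternative cause "an effect of another device, drug, treatment or other risk factors".

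Section 5.13.1 makes device-related and procedure-related adverse events separate reportable classes. On anticipated events, section 5.11.2 announces a list of effects of the study device and similar devices, and section 5.11.3 then describes its tables as "possible anticipated adverse events and possible adverse device effects associated with ablation catheters and closure devices".

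**The concern.** VERAFEYE is an add-on. Under section 5.10.3.3 it does not guide the treatment; under 5.4.2 it enters through femoral venous access; and under 5.11.4 it is likely to lengthen the procedure. Every subject therefore has two interventions in one session, and complications such as a groin haematoma or a pericardial effusion can come from either.

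The protocol asserts that VERAFEYE does not change the background risks (5.11.1) and that added time brings no greater risk of serious injury (5.11.4). With one arm and no comparator, case-by-case attribution is the main check on those assertions. If the procedure rating covers both interventions, or covers different things for different raters, it cannot serve as that check. The loss is hard to repair later, because attribution is a judgement made near the event with the case notes at hand.

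**Working it through.** No formula applies: the documents give no complication rate, endpoint or hypothesis, and the 40 subjects are not statistically derived (5.6, 5.7). The check is to compare how the term is used and then follow some events through the coding.

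**1. Scope of the term by section**

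- 5.10.3.1: the limit on operators for study procedures follows directly on the sentence about who performs the ablation or closure. Scope: the whole intervention.
- 5.11.1: the standard procedures are described as belonging to the study. Scope: includes the background intervention.
- 5.10.4: the visit is timed "not to exceed 2 days from the end of the study procedure". It also applies to attempt subjects, who under 5.9.2 had the imaging catheter inserted but no ablation or closure per protocol. Scope: cannot be the ablation or closure alone.
- 5.14.6: insured injury from study procedures is limited to harm that "would not have been expected from the standard treatment for a condition". Scope: harm beyond the background intervention.
- Table 8, first 'Not Related' criterion: device-use procedures only.
- Table 8, 'Not Related' lead-in and the possible, probable and causal rows: unrestricted.

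So the scope shifts between sections and also inside Table 8.

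**2. Events through the two ratings**

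- *Nerve injury from the ablation catheter.* Device: not related, since another device caused it. Procedure: related if the term includes the ablation. If it means device-use procedures, the alternative-cause criterion supports not related.
- *Haematoma attributed to VERAFEYE deployment.* Device: can be coded related, because the Adverse Device Effect definition in Table 6 includes deployment, operation and use error. Procedure: related on either reading.
- *Haematoma attributed to the ablation sheath.* Device: not related. Procedure: related on the broad reading, the same procedure code as the VERAFEYE haematoma.
- *Harm from longer procedure time because of imaging.* Device: arguable, as no device function caused it. Procedure: related, and indistinguishable from harm of the background intervention.

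The device rating separates the second event from the third. The procedure rating does not on the broad reading. On the narrow reading it does, but background harm is then not recorded as procedure-related at all. The fourth event has no clear place. Two raters, investigator and sponsor, could disagree on the first event purely over the meaning of the term.

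**3. Effect on reporting**

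A non-serious complication of the ablation belongs to the procedure-related class in 5.13.1 on the broad reading and may fall outside it on the narrow one. Serious events are reportable whatever their cause.

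**4. Anticipated events**

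Table 6 judges an Unanticipated Adverse Device Effect (UADE) against the investigational plan or application, and an Unanticipated Serious Adverse Device Effect (USADE) against the current risk assessment. Table 7 gives both 1 business day, against 3 calendar days for other serious events. Since 5.11.2 presents the lists as effects of the study device, a perforation caused by VERAFEYE could be argued to be already identified in the plan through Table 4, while the risk assessment might say otherwise. Two reference documents thus govern one reporting row.

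**The case against.** The strongest reply is that the plan already isolates device harm. Device relatedness has its own rating by both investigator and sponsor, its own reportable class and a broad definition, and it is named on the death form (5.13.3). Where relatedness cannot be assessed, Table 8 defaults to possible, which is conservative. This stands. A reader might infer that background and VERAFEYE complications cannot be separated at all; the documents do not support that. The loss is inside the procedure rating.

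A reader might also take Table 8 as a whole to mean device-use procedures. Only one criterion says so.

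Nor does the procedure rating drive the consequences one might attach to it. The 1-business-day clock depends on device association and anticipatedness, the study-termination circumstance in 5.14.10 concerns device-related complications, and insurance under 5.14.6 has its own test. Section 5.13.2.0.1 also says adverse events must always reach the sponsor through the CRFs, which softens the reporting gap, though it can be read as stating the route rather than widening the list in 5.13.1.

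On anticipated events, the USADE definition already uses the risk assessment, and Tables 4 and 5 carry titles naming the background procedures. That mitigates the problem but leaves the 5.11.2 lead-in and the two reference documents unreconciled.

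Finally, the AE CRF is not in the documents. Table 7 mentions only device relationship, as a non-exhaustive example, so the form may already hold more.

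**Conclusion.** The point holds as a defect of definition and resolution. The study procedure is undefined, its scope differs between sections and within Table 8, and the procedure rating pools VERAFEYE-specific steps with the background ablation or closure. The scope of the procedure-related reportable class is ambiguous as a result. The mismatch between 5.11.2 and Tables 4 and 5, and the differing UADE and USADE references, are a separate and smaller inconsistency.

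The size is qualitative. It touches descriptive safety tables for 40 subjects and consistency between raters; no test, sample size or endpoint is affected. The conclusion assumes that the AE CRF follows the two ratings in 5.13.2. If it already splits the procedure item, what remains is to align the protocol text. The documents do not say whether VERAFEYE needs its own venous puncture; if it shares an access site, attribution of access complications will remain uncertain even with a split.

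**What to change.** - Define 'study procedure' once and use it consistently.
- In 5.13.2, Table 8, the AE CRF and the death CRF, record relationship separately to (a) the VERAFEYE device, (b) VERAFEYE-specific procedures, meaning its venous access, catheter handling and added imaging time, and (c) the standard ablation or closure and its commercial devices. Tabulate events by all three.
- Align the narrow 'Not Related' criterion in Table 8 with these terms.
- Correct the 5.11.2 lead-in so that Tables 4 and 5 are identified as background-procedure events.
- Reconcile the reference documents for UADE and USADE.

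The cost is one extra CRF field and wording changes in a few sections, submitted as an amendment under 5.14.9. A few more events may be labelled VERAFEYE-related.

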5.13.2.0.2. Sponsor Reporting Requirements

The sponsor is responsible for reporting adverse event information to all participating Principal Investigators, ECs and regulatory authorities, as applicable. All events will be assessed by the Sponsor for relationship to study device and study procedure.

5.13.3. DEATH REPORTING

A subject death during the study should be reported to LUMA Vision no later than 3 calendar days of site notification. A detailed narrative (death letter) that provides detailed information describing the circumstances surrounding the death and cause of death should be submitted to the sponsor. In addition, a death case report form needs to be submitted to the sponsor, including the following details:

- Date and time of death
- Primary organ cause of death
- Timing of the death in relation to the procedure
- Whether or not the death was witnessed/monitored
- Whether the death was related to the procedure, or investigational device
- Autopsy report, if applicable

5.14. REGULATORY AND ETHICAL ASPECTS**5.14.1. STUDY FINANCING**

This study is financed by the Sponsor. The study site(s) shall enter into a clinical study agreement with the Sponsor that details the financing of the study as well as the rights and obligations of both the Sponsor and the site. The clinical study agreement must be executed before any participant is enrolled.

5.14.2. GENERAL DUTIES OF SPONSOR AND PRINCIPAL INVESTIGATOR**5.14.2.0.3. General Duties of Sponsor**

The Sponsor's general duties consist of submitting applications and information to appropriate regulatory authorities as required by local and national regulations, obtaining regulatory and EC approvals prior to allowing study start, selecting Investigators and ensuring proper clinical site monitoring.

**LUMINIZE_CLINICAL PROTOCOL**Document ID: VER-DOC-527
Controlled Document: VER-SIGN-3084TEMPLATE:
ONEPROJECTS/SIGN-267

Version: 4.0

Project: VERAFEYE (VER)
Date: 22-Nov-2024 14:16:10
Page: 42 / 51**5.14.2.0.4. General Duties of Principal Investigator**

It is the responsibility of the Principal Investigator to ensure that the study will be conducted according to the protocol, recognized ethical principles for medical research involving humans, principles of good clinical practice, (ICH-GCP), ISO 14155:2020 Clinical Investigation of medical devices for human subjects, principles of the "Declaration of Helsinki", any conditions of approval imposed by the reviewing EC and by the local regulation, if applicable.

The Principal Investigators will assure that all site personnel involved in the conduct of this study have completed ICH GCP Training as it pertains to this study. The protocol, informed consent form(s) and other related study materials will be submitted to the EC, and regulatory authority (as applicable) for review and approval. Approval of both the protocol and the consent form must be obtained before any participant is enrolled. Any additional requirements imposed by the EC or regulatory authority shall be implemented.

It is the responsibility of the Principal Investigator to ensure the following requirements are met before the start of the study:

- sign the Clinical Study Agreement, and comply with the Investigator responsibilities as described in such Agreement.
- sign the Investigator Brochure Signature Page and Protocol Signature page
- provide his/her recent curriculum vitae and that of site staff involved in the study
- insurance coverage for subjects in the study was obtained
- EC approval was obtained

It is the responsibility of the Principal Investigator to

- ensure that no deviations from this protocol occur, except if considered as needed to protect the life and physical well-being of a subject in an emergency. Any deviations that occurred during the study need to be documented, together with a rationale for the deviation.
- ensure that source documents and essential study documents throughout the clinical study are maintained and retained per requirements.
- ensure that the accuracy, completeness, legibility, and timeliness of the data reported to the sponsor in the CRFs and in all required reports
- record, report, and assess every adverse event as applicable per the protocol and observed device deficiency.
- report to sponsor, per the protocol requirements, all reportable events
- report to the EC and regulatory authorities any SAEs and device deficiencies that could have led to a SADE and potential UADE or USADE, as required by local/regional regulations
- maintain the device accountability records and control of the devices
- ensure that adequate facilities are available to perform the study
- ensure that informed consent is obtained in accordance with applicable laws, this protocol and local EC requirements (see section 21.4)
- allow the sponsor to perform monitoring and auditing activities.

**LUMINIZE_CLINICAL PROTOCOL**Document ID: VER-DOC-527
Controlled Document: VER-SIGN-3084TEMPLATE:
ONEPROJECTS/SIGN-267

Version: 4.0

Project: VERAFYE (VER)
Date: 22-Nov-2024 14:16:10
Page: 43 / 51

- regulatory authorities and ECs to perform auditing activities.

The Principal Investigator or his/her designee will take measures to prevent accidental or premature destruction of these documents.

5.14.2.0.4.1. Delegation of Responsibilities

The Principal Investigator may decide to delegate certain responsibilities to members of his/her site staff (Sub-Investigators, Clinical Research Coordinators and other site staff members, as applicable). These responsibilities shall then be appropriately documented prior to being performed. The Principal Investigator shall ensure his/her site staff is qualified and adequately trained prior to conducting any study-specific requirements. The Principal Investigator shall provide adequate supervision of those to whom tasks are delegated. Where there is a Sub-Investigator at a site, the Sub-Investigator cannot be delegated the primary supervisory responsibility for the site.

5.14.3. ROLE OF LUMA VISION REPRESENTATIVE(S)

LUMA Vision personnel can provide technical support to the investigator and other health care personnel (collectively HCP) as needed. Support may include HCP training, addressing HCP questions, or providing clarifications to HCPs concerning the operation of LUMA Vision's equipment/devices.

At the request of the investigator and while under investigator supervision, LUMA Vision personnel may operate equipment during the procedure, and interact with the subject to accomplish requested activities.

Typical tasks may include the following:

- Provide technical support or assist in the operation of the VERAFFEYE System and other supporting equipment based on instructions provided by the HCP during the procedure.
- Be present and have some direct contact with the patients at the procedure.
- After the procedure, review how the study equipment performed, and transfer pseudonymized data to the Sponsor's study database.
- Assist and review the collection of information about the procedure and study documents for completeness and accuracy.
- Complete the Technical Source Form during the procedure, in order to assist the HCP with data collection during the procedure.

LUMA Vision personnel will not do the following.

- Practice medicine
- Provide medical diagnosis or treatment to subjects
- Discuss a subject's condition or treatment with a subject
- Independently collect study data
- Enter data in electronic data capture systems or on paper case report forms

**LUMINIZE_CLINICAL PROTOCOL**Document ID: VER-DOC-527
Controlled Document: VER-SIGN-3084TEMPLATE:
ONEPROJECTS/SIGN-267

Version: 4.0

Project: VERAFYE (VER)
Date: 22-Nov-2024 14:16:10
Page: 44 / 51**5.14.4. ETHICS COMMITTEE**

The protocol, its modifications, and the patient consent forms will be reviewed and approved in writing by an Ethics Committee (EC) prior to initiation of the study. No changes can be made to the protocol or patient consent forms without Sponsor and EC approvals. No investigative procedures other than those defined in this protocol will be undertaken on the enrolled patients without the written agreement of the EC and Sponsor. The Principal Investigator will advise their EC of the progress of this clinical study according to EC reporting requirements. The EC must operate in accordance with the current national regulations.

